6.2 Adverse Events and Tolerability

Statistical analysis and reporting of adverse events will concentrate on treatment-emergent adverse events, i.e., all adverse events occurring between the start of treatment and end of the residual effect period, 7 days after the last dose of medication. Adverse events that start before first drug intake and deteriorate during the treatment period will also be considered as 'treatment-emergent'. All AEs will be listed, according to whether the AE start date occurred during the screening period, treatment period, or during the follow-up period.

The safety analyses will be purely descriptive statistics (*number and percentage, n (%)*) and will be based on the current version of Dictionary of Drug Regulation (MedDRA) coding system and display in tables and data listings using SOC and preferred term. The analyses will be provided for each cohort and also pooled across all cohorts. No hypothesis testing is planned. An overall summary of AEs will be presented, in addition the following tables will be produced by MedDRA SOC and preferred term:

- All AEs
- AEs by severity
- Serious AEs
- Drug-related AEs
- AEs leading to treatment discontinuation

In addition a summary of all AEs by investigator-defined category and MedDRA preferred term will be produced, the following categories will be included:

- Hypoglycaemic event
- Genital infection
- Acute pyelonephritis
- Sepsis
- Urinary tract infection
- Bone fracture
- Hepatic injury
- Ketoacidosis (metabolic acidosis, ketoacidosis, diabetic ketoacidosis)
- Decreased renal function
- Other

Further details on the specific AEs of hypoglycaemia, genital infections, acute pyelonephritis, sepsis, bone fractures and ketoacidosis will be listed. Additional summaries of these specific AEs and other specific AEs (e.g. volume depletion) may be produced dependent upon the frequency of occurrence.

6.3 Laboratory Data

Descriptive statistics (Mean (SD) and Median (IQR)) of the laboratory data will be presented. The presentation will cover data collected at screening or baseline to week 12 (screening to treatment period). Summaries of actual values at baseline and last value on-treatment along with the change from baseline will be tabulated for the individual parameter. Baseline data will be taken as the last available laboratory measurement on or prior to the day of starting study treatment. The individual patient values profile over time will be plotted. The marginal means of individual parameter will also be included in these plots. Laboratory values will be compared to their reference ranges at baseline and the last measurement on-treatment. Frequency tables will summarise the number of patients with potentially clinically significant abnormalities (as defined by BI project standards). Laboratory measurements taken up to 3 days after the last administration of randomised study treatment will be considered as on-treatment.

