#### 1.4 BENEFIT - RISK ASSESSMENT

The overall benefits and safety profile of empagliflozin have been outlined in previous sections. A pharmacologic rationale for the use of empagliflozin in HF can be found in [Section 1.1](#). The overall tolerability and safety profile outlined in [Section 1.2](#), and the current IB, supports chronic administration of empagliflozin 10 mg in human studies.

Investigators will be encouraged to treat participants to best standard of care in compliance with the local guidelines and recommendations for HF, and Diabetes Mellitus (DM) if present. Based on the putative mechanism of actions (reviewed in [Section 1.3](#)) and the result of the EMPA-REG OUTCOME trial, it is assumed that patients with HF should benefit from empagliflozin treatment on top of guideline-directed therapies. The safety profile of empagliflozin in these patients is expected to be comparable to that previously observed in over 10,000 patients with T2DM treated with empagliflozin, including patients with high CV risk. Safety will be ensured by close monitoring of the subjects for AEs both clinically and by laboratory testing. Special attention will be paid to prevent metabolic acidosis, ketoacidosis and diabetic ketoacidosis (DKA). For further details refer to [Section 4.2.1](#).

As with all drugs, the potential for hypersensitivity and allergic reactions has to be taken into consideration when empagliflozin is administered. Other risks to the patients are the risks inherent to any investigational medicinal product used in a clinical trial setting, such as unexpected adverse clinical or laboratory events.

Some of the assessment techniques used in this trial are not standard in heart failure patients. Patients will be provided with full information about the anticipated risks of these procedures to enable them to make an informed decision about participation.

Empagliflozin causes intravascular volume contraction. In patients with volume depletion, correcting this condition prior to initiation of empagliflozin is recommended.

Although rare, a potential for drug induced liver injury (DILI) is under constant surveillance by the Sponsor and regulators. Therefore this trial requires timely detection, evaluation and follow-up of laboratory alterations in selected liver laboratory parameters to ensure patients' safety, see also [Section 5.3.5.1](#).

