#### **Hepatic injury**

A hepatic injury is defined by the following alterations of hepatic laboratory parameters, when observed at any timepoint after randomisation:

- an elevation of AST and/or ALT  $\geq 3$  fold ULN combined with an elevation of total bilirubin  $\geq 2$  fold ULN measured in the same blood draw sample, and/or
- aminotransferase (ALT, and/or AST) elevations  $\geq 5$  fold ULN

These laboratory findings constitute a hepatic injury alert and the patients showing these lab abnormalities need to be followed up according to the “DILI checklist” provided in the ISF.

In case of clinical symptoms of hepatic injury (icterus, unexplained encephalopathy, unexplained coagulopathy, right upper quadrant abdominal pain, etc.) without laboratory results (ALT, AST, total bilirubin) available, the investigator should make sure these parameters are analysed, if necessary in an unscheduled blood test. Should the results meet the criteria of hepatic injury alert, the procedures described in the DILI checklist should be followed.

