#### **7.3.4 Safety analyses**

Adverse events will be coded using the Medical Dictionary for Drug Regulatory Activities (MedDRA). Standard ARO summary tables and listings will be produced. All adverse events with an onset between start of treatment and end of the residual effect period (REP), a period of 7 days after the last dose of trial medication, will be assigned to the on-treatment period for evaluation.

All treated patients will be included in the safety analysis. In general, safety analyses will be descriptive in nature and will be based on BI standards. No hypothesis testing is planned.

Statistical analysis and reporting of adverse events will concentrate on treatment-emergent adverse events, i.e. all adverse events occurring between start of treatment and end of the residual effect period. Adverse events that start before first drug intake and deteriorate under treatment will also be considered as ‘treatment-emergent’.

Frequency, severity, and causal relationship of adverse events will be tabulated by system organ class and preferred term after coding according to the current version of the Medical Dictionary for Drug Regulatory Activities (MedDRA) at the database lock.

Laboratory data will be analysed both quantitatively as well as qualitatively. The latter will be done via comparison of laboratory data to their reference ranges. Values outside the reference range as well as values defined as clinically relevant will be summarised. Treatment groups will be compared descriptively with regard to distribution parameters as well as with regard to frequency and percentage of patients with abnormal values or clinically relevant abnormal values.

Vital signs, physical examinations, or other safety-relevant data observed at screening, baseline, during the course of the trial and at the end-of-trial evaluation will be assessed with regard to possible changes compared to findings before start of treatment.

The details of the analysis will be specified in the TSAP.

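### SAP 6.3 checks laboratory values against reference ranges only at baseline and the last on-treatment sample, so a transient abnormality seen in an extra sample can drop out of that comparison

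*SAP*

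**What the plan says.** SAP 6.3 (Laboratory Data) specifies these outputs and one window:

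- Descriptive and change tables: "Summaries of actual values at baseline and last value on-treatment along with the change from baseline will be tabulated for the individual parameter".
- Reference-range comparison: "Laboratory values will be compared to their reference ranges at baseline and the last measurement on-treatment".
- A count of more serious abnormalities: "Frequency tables will summarise the number of patients with potentially clinically significant abnormalities (as defined by BI project standards"). No time point is given for this table.
- A figure: "The individual patient values profile over time will be plotted".
- The window: "Laboratory measurements taken up to 3 days after the last administration of randomised study treatment will be considered as on-treatment".

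Protocol 7.3.4 (Safety analyses) says: "Values outside the reference range as well as values defined as clinically relevant will be summarised". It adds that the groups will be compared descriptively on the number and percentage of patients with abnormal or clinically relevant abnormal values. It does not mention the last sample, and it leaves the detail to the SAP.

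SAP 1.4, which lists changes to the planned analysis, mentions only the baseline covariate. SAP 6.2 plans an adverse event table by category that includes hepatic injury and decreased renal function.

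**The concern.** A last-value rule shows where each patient ended, not whether the patient was abnormal at any time on treatment. For a safety table the second question is usually the one of interest, and it is the more natural reading of a protocol that speaks of patients with abnormal values.

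The rule also acts selectively. Extra blood samples are not drawn at random. For suspected liver injury, for example, the protocol says that "the investigator should make sure these parameters are analysed, if necessary in an unscheduled blood test". Where a problem prompts repeat testing and then resolves, the later value is the one that enters the comparison.

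At stake is the completeness of one descriptive table and its agreement with the other safety outputs. A patient could be counted under hepatic injury in the adverse event categories and yet appear as normal at baseline and normal on treatment in the reference-range table, with nothing in the SAP to explain the difference.

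**Working it through.** There is no planned figure to reproduce. The check is to set the sampling schedule against the rule.

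**Inputs**

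1. Safety blood is scheduled at Visits 1, 2 and 4 (Protocol flowchart). Visit 3 requires only a urine ketone test (flowchart footnote 3). Scheduled safety blood samples after the first dose: 1.
2. All Visit 4 assessments fall within 48 hours of the last dose (Protocol 6.2.2), inside the 3-day on-treatment window of SAP 6.3.
3. Unscheduled samples are possible: liver tests when symptoms suggest hepatic injury, follow-up of a hepatic alert under a checklist, and renal follow-up by local guidance (Protocol 5.3.5.1).

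**Last value against worst value, by sampling pattern**

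| On-treatment samples | Last value | Worst value | Missed in the reference-range comparison? |
|---|---|---|---|
| Visit 4 only | Visit 4 | Visit 4 | No, they are identical |
| Extra sample normal, Visit 4 abnormal, no repeat | abnormal | abnormal | No |
| Extra sample abnormal, Visit 4 normal | normal | abnormal | Yes |
| Visit 4 abnormal, normal repeat within 3 days of last dose | normal | abnormal | Yes |
| Visit 4 abnormal, normal repeat later than 3 days after last dose | abnormal (Visit 4) | abnormal | No, the repeat is outside the window |

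The fourth row has little room. If Visit 4 blood is drawn on the day of the last dose, up to 3 days remain. If it is drawn at the 48-hour limit, 3 − 2 = 1 day remains. Safety samples go to a central laboratory (Protocol 5.3.3), and no turnaround time is stated. The third row is the more plausible route.

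**What the other outputs recover**

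- *Adverse event categories (SAP 6.2).* Hepatic injury is defined at any time after randomisation, and decreased renal function by a creatinine threshold (Protocol 5.3.5.1). Both are events of special interest with 24-hour reporting, so they should be counted in the category table whatever the last sample shows.
- *Other adverse events.* A laboratory change below those thresholds is recorded as an adverse event only if the investigator judges it clinically relevant (Protocol 5.3.5.2). The rest depend on the laboratory tables.
- *Clinically significant abnormalities (SAP 6.3).* The text does not restrict this table to the last value, but nor does it say which on-treatment value is used. The definition lies in project standards that are not in the documents.
- *Profile plots.* These could show a transient peak but give no counts, and the SAP does not say whether unscheduled values are plotted.

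The gap is therefore an out-of-range value, seen in an extra sample, normal again by the last on-treatment sample, and below the event-of-special-interest and project thresholds. A possible disagreement between tables for patients above those thresholds comes in addition.

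**The case against.** The case for leaving the text alone has several sound parts.

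- *Reach.* With one scheduled post-dose blood sample, most patients may have only one on-treatment value. This stands. The rule is harmless for all of them.
- *Serious events are captured elsewhere.* This stands for events meeting the special-interest definitions, provided they are reported as required. A reader might infer from SAP 6.3 that an abnormality is lost from the safety tables altogether, or that a liver or kidney event of special interest could go uncounted. The documents do not support that: SAP 6.2 counts those categories, and the clinically significant table carries no last-value limit.
- *The protocol delegates detail to the SAP.* This is partly right. Protocol 7.3.4 specifies neither worst nor any value, so the SAP narrows the plan rather than contradicting it. The narrowing is still real and is not recorded in SAP 1.4.
- *Mechanism.* How often an alert leads to repeat blood tests depends on a checklist in the site file and on local guidance, neither of which is available. This stands and prevents any estimate of frequency.
- *Purpose.* Protocol 1.4 says "Therefore this trial requires timely detection, evaluation and follow-up of laboratory alterations in selected liver laboratory parameters". That concerns clinical detection and follow-up, not tabulation. It shows that liver values matter to the sponsor, but it does not prescribe a worst-value table.
- *Weight.* The protocol declares no safety endpoints, and safety is summarised without hypothesis tests. This stands and sets the severity.

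None of this makes the last value the better choice for a comparison meant to show which patients had abnormal results.

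**Conclusion.** The point holds in a limited form. SAP 6.3 ties the reference-range comparison to baseline and the last on-treatment sample, which is narrower than the frequency of patients with abnormal values foreseen in Protocol 7.3.4. In patients with unscheduled or repeat on-treatment samples, a transient out-of-range value that has normalised by the last such sample is missed in that comparison. In patients with scheduled samples only, the effect is nil.

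The size cannot be estimated, because the documents do not say how many extra samples are expected. The conclusion assumes that some are taken and that their results reach the trial database. Severity is low: a descriptive table is affected, and the efficacy conclusion does not depend on it.

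**What to change.** In SAP 6.3:

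1. Base the reference-range comparison on the worst on-treatment value per patient and parameter, including unscheduled and repeat samples within the on-treatment window. Where both directions matter, report values below and above the range separately.
2. State that the table of potentially clinically significant abnormalities counts a patient with any qualifying on-treatment value, again including unscheduled and repeat samples.
3. Keep the last on-treatment value for the change-from-baseline summary, where one consistent late time point is appropriate.

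The cost is a sentence or two in the SAP and a small programming change. No new data are needed and patient management is unaffected. The drawback is that patients sampled more often have more chances to show an abnormal value, so a difference between arms in extra sampling could feed into the counts. Reporting the number of patients with extra on-treatment samples by arm would let a reader judge this.

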6.4 Vital Signs, Electrocardiogram, and Other Safety Assessments

[figure not shown]
Vital signs, ECG and other safety assessments will be summarised descriptively.

[figure not shown]
7 Data Handling Conventions

[figure not shown]
7.1 Data Quality Assurance and Monitoring

For the data monitoring and quality assurance procedures for the study, see the study in Protocol (1245.148) Section 8.2 – Section 8.7

9.1 Appendix 1: Reporting Conventions

- This section clarifies the reporting conventions adopted or utilized in the SAP related statistical operations that could be utilized in the reporting of the study.
- All tables, listings and figures will be presented in landscape orientation unless there is a specific reason to use portrait orientation.

9.2 Appendix 2: Important Protocol Deviations (iPDs)

The IPDs listing below is taken from the Medical and Quality Review Plan document, Version 2.0, dated 27th February 2018, for Study 1245-0148. The listing is tentative and subject to a review before the data lock. The updated version of the IPDs listing in the Medical and Quality Review Plan document will be used for the statistical analyses and the CTR.

Category / Code	Description	Requirements	Excluded from
A	Entrance criteria not met		
A1	Target indication not met		
A1.06	No chronic HF NYHA class II-IV	Inclusion criterion #2 violated	<None or PPS>
A1.07	Conditions on ejection fraction (EF) violated	Inclusion criterion #7 for Cohort A, #10 for Cohort B violated	PPS
A1.08	Conditions on NT-proBNP violated	Inclusion criterion #8 for Cohort A, #11 for Cohort B violated	PPS
A1.09	Conditions on HF violated	Inclusion criterion #1 and #9 for Cohort A, or #1 and #12 for Cohort B violated	PPS
A2	Inclusion criteria not met		
A2.02	Age out of range	Inclusion criterion #4 violated	None
A2.08	Specific inclusion criterion for women of child-bearing potential violated	Inclusion criterion #5 violated	None
A3	Exclusion criteria not met		
A3.44	Patient with unstable conditions	Exclusion criteria #1, #2, #4, #7, #11, #14, #15, #16 or #20 violated	None
tba	All other in/exclusion criteria		Individual discussion
B	Informed consent		
B1	Informed consent not available/not done	Informed consent date missing or inclusion criterion #6 violated	PPS
B2	Informed consent too late	Informed consent date was after Visit 1	None
C	Trial medication and randomisation		
C1	Incorrect trial medication		

	C1.02	Incorrect trial medication taken	Medication from wrong treatment arm taken for more than 20% of the overall treatment duration Can only be finally judged after data base lock (DBL) since unblinding information is required.	None
C2		Randomisation not followed		
	C2.01	Treated without randomisation	Patient treated according to eCRF, but not randomised according to IVRS.	None
C3		Non-compliance		
	C3.01	Non-compliance with study drug intake	Overall study treatment compliance outside 80% and 120% (exclusive) or study treatment compliance below 80% Missing compliance will be considered iPD.	None
C4		Medication code broken		
	C4.01	Medication code broken at site without just cause	Medication code was broken for no valid reason. Final decision at the DBL meeting based on medical judgement.	None
D		Concomitant medication		
	D1.02	Use of other investigational drug	Review of eCRF for prohibited medication. Final decision at the DBL meeting based on medical judgement.	None
	D2.01	Use of protocol defined prohibited medication during treatment period	Use of SGLT-2 or combined SGLT-1 and 2 – inhibitors after randomization until the follow-up visit.	None
E		Missing data		
	E1.05	No baseline resting ³¹ P MRS result	No valid baseline PCr/ATP ratio at resting and dobutamine stress.	PPS
	E1.06	No baseline stress ³¹ P MRS result	No valid baseline PCr/ATP ratio at dobutamine stress.	PPS
F		Other		
	F1.02	Other PD related to safety only	Manually detected, safety related protocol deviations Final decision at the DBL meeting based on medical judgement.	None
	F1.03	Other PD related to primary endpoint	Final decision at the DBL meeting based on medical judgement.	PPS

	F1.04	Other PD related to patient rights	Manually detected protocol deviations related to patient rights Final decision at the DBL meeting.	None
--	-------	------------------------------------	---	------

APPROVAL / SIGNATURE PAGE**Document Number: c32019191****Technical Version Number:1.0****Document Name: 8-01-tsap-core-v2-2020-03-12****Title: 8-01-tsap-core-v2-2020-03-12****Signatures (obtained electronically)**

Meaning of Signature	Signed by	Date Signed
-----------------------------	------------------	--------------------

Approval-Biostatistics

21 Apr 2020 14:15 CEST

(Continued) Signatures (obtained electronically)

Meaning of Signature	Signed by	Date Signed
-----------------------------	------------------	--------------------

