#### **2.1.2 Primary endpoint**

The primary endpoint is the change from baseline to week 12 in PCr/ATP ratio in the resting state measured by P MRS.

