### Cardiac MR spectroscopy (P MRS and proton MRS)

#### P MRS (rest and dobutamine stress)

Rest P MRS will be performed to obtain the PCr/ATP ratio from a voxel placed in the midventricular septum, with the subjects lying prone with their heart over the centre of the phosphorus coil in the iso-centre of the magnet as previously described [[R17-0693](#)]. After resting spectroscopy, dobutamine will be infused intravenously at incremental rates between 5 and 40 mcg/kg with a target of 65% of age maximal heart rate. During this time, blood pressure will be measured every minute. Heart rate, pulse oximetry, and ECG will also be monitored continuously during both dobutamine infusion. Heart rate will be maintained at target for the duration of the scans (8-10 minutes for 31P-MRS) [[R17-0697](#)]. Where possible, additional cine imaging will be acquired at rest and during dobutamine stress for assessment of cardiac function.

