### 7.3 PLANNED ANALYSES

Adherence to the protocol (such as inclusion/exclusion criteria, times of measurement, compliance with intake of trial medication, treatment dispensing errors, prohibited concomitant medication, completeness and consistency of data) will be checked. Important protocol violations (IPVs) will be identified no later than in the Blinded Report Planning Meeting and provided in the TSAP.

The following analysis sets will be defined for this trial:

- Randomised set (RS):  
This subject set includes all randomised patients, whether treated or not.
- Treated set (TS):

This patient set includes all subjects from the RS who were documented to have received one dose of study drug. This is the Intent to treat (ITT) population.

- Per-protocol set (PPS):  
This patient set includes all patients from the TS who provide evaluable data at baseline and on-treatment for the primary endpoint and are not affected by protocol violations relevant to the statistical evaluation of the primary endpoint.

Whether a primary endpoint data is evaluable or a protocol violation is relevant will be decided no later than at the final Blinded Report Planning Meeting (BRPM).

Relevant protocol violations may include:

- Use of prohibited medication
- Patient was non-compliant to study drug intake (e.g.: study drug compliance <80%)

For both efficacy and safety analyses, treatment will be evaluated as treated.

Baseline will be defined as the last available measurement before start of randomised trial medication.

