2.1 Primary Endpoints

2.1.1 Definition and Derivation of Primary Endpoint

The primary endpoint is the change from the baseline to week 12 in PCr/ATP ratio in resting state measured by ^{31}P MRS after treatment with Empagliflozin or matching placebo.

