3.1 Per-protocol Set (PPS)

The primary endpoint analysis will be performed using the per protocol (PP) set of patients having a valid PCr/ATP ratio measurements available at baseline and week 12, and not having an important protocol violation relevant to the primary endpoint. Protocol violations will be reviewed by the study team before the database lock to determine which violations disqualify a patient from the Per-Protocol analysis. A preliminary list of criteria that may disqualify a patient from the Per-Protocol analysis are presented in Section 9.2 in the SAP. The list is suggestive and subject to change at the final Blinded Report Planning Meeting (BRPM) pre-lock review.

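### SAP Appendix 9.2 lists a missing baseline stress PCr/ATP ratio (E1.06) as a per-protocol exclusion, although the primary endpoint uses only the resting ratio

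*SAP*

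**What the plan says.** Protocol 2.1.2 defines the outcome: "The primary endpoint is the change from baseline to week 12 in PCr/ATP ratio in the resting state". SAP 2.1.1 agrees: "The primary endpoint is the change from the baseline to week 12 in PCr/ATP ratio in resting state".

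The per-protocol set is built on that endpoint in both documents. Protocol 7.3 takes treated patients who "provide evaluable data at baseline and on-treatment for the primary endpoint" and who have no violation bearing on its evaluation. SAP 3.1 requires valid PCr/ATP measurements at baseline and week 12 and "not having an important protocol violation relevant to the primary endpoint".

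The deviation list in SAP Appendix 9.2 has two rows on missing baseline spectroscopy, both marked PPS under exclusions. E1.05 is titled as the missing resting result. E1.06 is titled as the missing stress result, and its requirement is "No valid baseline PCr/ATP ratio at dobutamine stress".

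On the status of the list, SAP 3.1 states: "The list is suggestive and subject to change at the final Blinded Report Planning Meeting (BRPM) pre-lock review". The introduction to Appendix 9.2 adds: "The updated version of the IPDs listing in the Medical and Quality Review Plan document will be used". That updated version is not among the documents.

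**The concern.** E1.06 applies a stress-scan criterion to an analysis set that exists for a resting-scan endpoint. The stress ratio is neither the response nor a factor in the primary model in SAP 5.3.1, so its absence says nothing about whether a patient can be evaluated for the primary endpoint.

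The row has consequences only for patients whose resting data are sound, because patients without a valid resting baseline are already removed by SAP 2.1.3 and SAP 3.1. Its only effect would be to take usable patients out of the primary test. In a cohort planned around 30 evaluable patients, with power just above the 80% target, a few such losses matter.

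**Working it through.** **Consistency check**

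1. The endpoint is resting PCr/ATP only (Protocol 2.1.2, SAP 2.1.1).
2. A PPS exclusion needs either missing primary-endpoint data or a violation relevant to that endpoint (Protocol 7.3, SAP 3.1).
3. The stress scan comes second. Protocol 5.2.4 says: "After resting spectroscopy, dobutamine will be infused intravenously". A stopped or unusable stress scan can therefore leave a valid resting baseline.
4. Take a patient with valid resting ratios at baseline and week 12, no stress ratio at baseline and no other deviation. Protocol 7.3 and SAP 3.1 keep this patient in the PPS; E1.06 marks the same patient for exclusion. The two cannot both apply.
5. Protocol 6.2.2 requires all Visit 2 assessments before the first dose, so treatment cannot affect whether the baseline stress scan succeeds. The loss is expected to cost precision and not to bias the comparison.

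**The plan's own sample size**

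Inputs from Protocol 7.7: difference 0.3, SD 0.28, two-sided alpha 0.05, 80% power, 30 evaluable per cohort, 30% drop-out. Allocation is 1:1 (Protocol 7.6).

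- Two-sample t-test, df = N − 2: 14 per arm gives 77.9% power and 15 per arm gives 80.8%. So 15 per arm, 30 in total, is reproduced.
- 30 / (1 − 0.30) = 42.9, which rounds up to 43, also reproduced.

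**Illustration of the cost**

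The documents give no rate of failed stress scans, so a loss of 1, 2 or 3 of 30 evaluable patients is assumed. The model has treatment plus two yes/no factors, so df = N − 4.

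- SE = 0.28 × √(1/n₁ + 1/n₂)
- Noncentrality = 0.3 / SE, with power from the noncentral t distribution
- 95% CI half-width = t(0.975, N − 4) × SE
- Number to randomise to keep 30 evaluable, if the 30% allowance does not already cover missing stress scans: 30 / (0.7 × (1 − k/30)), where k is the number lost

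| Lost (k) | n₁/n₂ | SE | t | Power | Half-width | Randomised to keep 30 |
|---|---|---|---|---|---|---|
| 0 | 15/15 | 0.1022 | 2.056 | 80.6% | 0.210 | 42.9 → 43 |
| 1 | 15/14 | 0.1041 | 2.060 | 79.1% | 0.214 | 44.3 → 45 |
| 2 | 14/14 | 0.1058 | 2.064 | 77.6% | 0.218 | 45.9 → 46 |
| 3 | 14/13 | 0.1078 | 2.069 | 75.9% | 0.223 | 47.6 → 48 |

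The power and half-width columns apply if the cohort is not enlarged. The last column applies if it is, and power is then kept. All values there lie below the cap of 60 in Protocol 7.7.

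**The case against.** The strongest reply is that the row does not operate by itself. Appendix 9.2 copies a plan dated 27 February 2018, before both protocol amendments, and still has unsettled entries. The study team decides at the blinded meeting which violations disqualify a patient, and a team applying SAP 3.1 correctly would drop E1.06 unprompted. This stands as a limit: the row is a draft entry to correct, not a settled exclusion. But it survives in a SAP approved in April 2020, and the pre-lock review is where it would either be corrected or carried forward.

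A second reply concerns origin. Protocol 7.3.1 assigns the PPS to cardiac energetics endpoints in the plural, and Protocol 5.2.4 counts both rest and stress ratios as cardiac energetics. E1.06 may therefore have been meant to mark patients who cannot be evaluated for stress. That is plausible, but PPS membership is set per patient, so the row would remove them from the resting analysis too. SAP 3.2 moreover places exploratory endpoints on the randomised set with available data. The difference between Protocol 7.3.1 and SAP 3.2 on the stress analysis set is a separate matter, which correcting this cell does not settle.

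Third, the impact may be small. Exclusion criterion 3 already removes patients with a contraindication to the dobutamine test, the cohort may be enlarged, and a sensitivity analysis on the randomised set could include these patients. All of this stands and limits the size of the problem. However, SAP 3.2 ties that sensitivity analysis to a substantial number of violations, whereas Protocol 7.3.1 states it without condition, and in either case the primary test would not use these patients.

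**Conclusion.** The concern holds. E1.06, as listed, conflicts with the per-protocol definitions in Protocol 7.3 and SAP 3.1 and could remove patients with complete primary data. It should be fixed before lock.

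The conflict rests on the text alone and needs no assumption. The size does: it depends on an unknown number of patients with a valid resting scan and no valid stress scan at baseline. Under the assumed losses of 1 to 3 patients, power falls by 1.5 to 4.7 percentage points (80.6 − 79.1 and 80.6 − 75.9), or 2 to 5 more patients are randomised per cohort (45 − 43 and 48 − 43). If the 30% drop-out allowance already covers missing stress scans, no extra recruitment is needed. Even one loss in a cohort of 30 that is not enlarged takes power just below the planned 80%.

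**What to change.** At or before the blinded pre-lock review, change the exclusion entry for E1.06 from PPS to None in the updated deviation list of the Medical and Quality Review Plan. Patients without a baseline stress ratio are then left out of the stress PCr/ATP analysis only.

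As an editorial matter, reword the E1.05 requirement to refer to the resting ratio alone. Its title names the resting result, but its text names rest and stress together. This admits no one to the PPS, since SAP 2.1.3 and 3.1 already require a valid baseline measurement.

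The cost is one table cell and one line of wording. Data collection is unchanged, and a change made while blinded cannot be driven by the results.
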